Day	-56 to -7	-14 to -7	1	29 (±2)	57 (±3)	85 (±3)	89 (-4)	92 (±3)	99 (±3)	106 (±3)	113 (±3)	117 (-4)	120 (±3)	127 (±3)	134 (±3)	141 (±3)	145 (-4)	148 (±3)	155 (±3)	162 (±3)	169 (±3)		
HBV DNA quantitative	Х		Х			Х					Х										Х	Х	Х
Total HBsAg ⁱ			Х			Х					Х					Х					Х	Х	
HBcrAg			х	Х	Х	Х					Х			Х		Х			Х		Х	Х	
Total anti-HBc quantitative			х			х					х					х					х		
HBV RNA quantitative			х	х	х	Х					х			х		Х			х		х	Х	
HBV RNA sequencing ^h			х																				
HBV DNA sequencing ^j																						Х	
Plasma PK (siRNA) k			х				Х										Х				х	Х	
Plasma PK (PD-L1 LNA) k						Х										Х					х	Х	
Plasma PK (NUC) k			х			х										х					х	x	
Plasma ADA (siRNA) ^I			х				Х										Х				Х	Х	Х
Plasma ADA (PD-L1 LNA) ^I						х										x					х	x	х
Liver injury markers			х			Х			х		х			Х					Х			х	
Extracellular vesicles			х			Х					х			Х		Х			Х		Х		х
Circulating immune phenotyping			х			х					х			Х		х			х		х		х
Soluble PD-L1			х	Х	Х	Х					х			Х		Х			Х		Х	•	Х
Cytokine panel ^m			х	Х	Х	Х					х					Х					Х		Х
PBMC ⁿ			Х			Х															Х		
FNA °			х	•		х															х		

Appendix 13-*Table 7* Schedule of Activities for siRNA + PD-L1 LNA + NUC Treatment Arm – 24 Week (Screening and Treatment Periods) (cont.)

	Scree	ning									Tre	eatme	nt Perio	od								VB/ VR	ET/ UV ^u
Week			1	5	9	1	3	14	15	16	17	7	18	19	20	2	1	22	23	24	25		
Day	-56 to -7	-14 to -7	1	29 (±2)	57 (±3)	85 (±3)	89 (-4)	92 (±3)	99 (±3)	106 (±3)	113 (±3)	117 (-4)	120 (±3)	127 (±3)	134 (±3)	141 (±3)	145 (-4)	148 (±3)	155 (±3)	162 (±3)	169 (±3)		
Liver Biopsy ^p																					Х		
RBR ^q			Х			х										Х					Х	х	
Clinic siRNA 200 mg sc Q4W treatment administration r			х	х	х		χ ^r					χ ^r					X ^r						
Clinic PD-L1 LNA sc treatment administration r, s																							
NUC treatment administration OD													х										
Adverse events, concomitant medications, and diary review ^t			х	х	х	х		х	х	х	х		х	х	х	x		х	х	х	х	х	x

Appendix 13-*Table 7* Schedule of Activities for siRNA + PD-L1 LNA + NUC Treatment Arm – 24 Week (Screening and Treatment Periods) (cont.)

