4.1 GENERAL CONSIDERATIONS

Disposition and protocol deviations listings and summaries will be based on all randomized participants. Analysis of safety will be based on the safety population. Pharmacodynamics and efficacy analysis will be based on the modified intention-to-treat (mITT) population. Pharmacokinetic analysis will be based on PK population. Immunogenicity analysis is based on the immunogenicity population.

For the treatment arms where additional patients have been recruited to proactively mitigate any impact of COVID-19 or force majeure events, the primary analysis will be performed when approximately 30 patients considered evaluable for the primary analysis reach the primary endpoint of Week 24 post EOT. If the primary analysis is positive for an experimental treatment arm, any additional patients that have been recruited to that treatment arm, will continue and be included in the final CSR.

Evaluable patients: A patient from the mITT population will be considered 'evaluable' if no more than two consecutive siRNA missing doses due to non-safety reasons (e.g., COVID-19 disruptions). This is based on the siRNA liver half-life of ~10 weeks.

estimated from ph1 data. Therefore, after two consecutive missing doses the drug left in the liver is expected to be \sim 40%, which was considered adequate as patients would restart dosing so up to 2 missing doses are not expected to have a major impact on the efficacy.

Evaluable patients in mITT population will be used to estimate the primary endpoint/estimand.

Any subject who does not have a virology parameter evaluation during the pre-specified window for 24-week Follow-up visit (either due to missing assessment or due to early withdrawal from the study or study treatment) will be considered as a non-responder. However, if the subject with missing evaluation is a responder both before and after the visit window, then the subject will be categorized as a responder for that visit.

Key definitions:

The following definitions will be used:

Baseline: The baseline value is defined as the last available valid (quantifiable continuous or categorical value), non-missing observation for each participant prior to first study drug administration. Repeat and unscheduled assessments will be included in the derivation of the baseline values.

HBsAq Loss: HBsAg loss refers to a negative/undetectable HBsAg level, HBsAg loss is defined HBsAg levels <0.05 IU/mL.

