4.6 OTHER ANALYSES

4.6.1 Summaries of Conduct of Study

The number of participants who were randomized, discontinued treatment, completed treatment, discontinued study and completed the study (including follow-up period) will be summarized by treatment. Major protocol deviations will be summarized and listed by each treatment arm. Separate listing will be provided for the patients who have met the NUC discontinuation criteria at EOT or follow-up but have not stopped NUC (reluctant to do).

For each participant assessment, the baseline value will be the latest non-missing assessment prior to the first dose administration, this being study Day 1 pre-dose. In the absence of data on study Day 1, the latest non-missing value collected during screening will be used, if such data are not available then the assessment baseline value will be missing for that participant.

4.6.2 Summaries of Treatment Group Comparability/Demographics and Baseline Characteristics

Descriptive statistics will be generated for demographic and baseline disease characteristics including sex, race, ethnicity, origin (for Asian participants only), age, weight, height, body mass index, HBV DNA and HBsAg levels, and HBV history including but not limited to duration of HBV disease, likely route of transmission, HBV genotype, HBeAg status, previous HBV treatments (including incidence of Peg-IFN), and length of time on NUCs.

For NUC treatment duration calculation, if there is a break of treatment of less than 6 months then the duration will be cumulative, if break of treatment is more than 6 months, then the last continuous course of treatment with any nucleos(t)ide products prior to baseline (categorized as <3 years, >=3 to <5 years, >=5 years to <10 years, and >=10 years) will be counted. The effect of this duration covariate will be examined with respect to efficacy, immunogenicity, and antiviral endpoints in separate analyses.

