4.6.3 Pharmacokinetic Analyses

The analysis of PK variables will be conducted by Clinical Pharmacology and reported in the CSR.

4.6.4 Immunogenicity Analyses

The analyses will be carried out on the immunogenicity analysis population

The numbers and proportions of ADA-positive participants and ADA-negative participants at baseline (baseline prevalence) and after study drug administration (post-baseline incidence during both the treatment and follow-up periods) will be summarized.

 Participants are considered to be ADA positive if they are ADA negative at baseline but develop an ADA response following study drug administration (treatment-induced ADA response), or if they are ADA positive at baseline and the titer of one or more post-baseline samples is greater than the titer of the baseline sample by a scientifically reasonable margin such as at least 4-fold (treatment-enhanced ADA response).

 Participants are considered to be ADA negative if they are ADA negative at baseline and all post-baseline samples are negative, or if they are ADA positive at baseline but do not have any post-baseline samples with a titer that is greater than the titer of the baseline sample by a scientifically reasonable margin such as at least 4-fold (treatment unaffected).

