5.2 APPENDIX 2 ANALYSIS DETAILS SPECIFIC TO TLR7 TREATMENT COMBINATION

TLR7 treatment combination arm specific analysis are listed in this appendix.

Immune Pharmacodynamics Biomarker Analysis: Markers of Humoral and Cellular Response

PD biomarker variables measured are listed in Table 7 below.

Table 7 List of Immune PD biomarker variables

Туре	Variable	Label	Unit
Transcriptional	TLR7	TLR7	delta Ct*
Transcriptional	OAS-1	OAS1	delta Ct*
Transcriptional	MX1	MX1	delta Ct*
Transcriptional	ISG-15	ISG15	delta Ct*
Serum soluble protein (cytokine)	IFN-α	IFN-alpha	ng/L
Serum soluble protein (cytokine)	IFN-γ	IFN-Gamma	ng/L
Serum soluble protein (cytokine)	IP-10	IP-10	ng/L
Serum soluble protein (cytokine)	TNF-α	TNF-alpha	ng/L
Serum soluble protein (cytokine)	IL-6	IL-6	ng/L
Serum soluble protein (cytokine)	IL-1	IL-1	ng/mL
Serum soluble protein (cytokine)	IL-10	IL-10	ng/L

^{*} delta Ct will be provided by the lab performing the analysis.

For each PD variable, descriptive statistics will be presented separately by treatment arm, appropriate TLGs will be produced as listed below.

- 1) Descriptive Statistics- N, Mean, SEM, SD, Median, Min, Max
- Geometric Mean and Change from baseline (baseline for the period) for each time point- tables and plots
- 3) Plot of Absolute Values over Time
- 4) Fold Change (FC) from BL for each time point tables and plots

Cytokine and Neopterin Variables:

Combination Therapies for CHB—F. Hoffmann-La Roche Ltd Statistical Analysis Plan WV41073

- Log10 for each variable at each time point
- Fold change from baseline for each time point based upon raw data
- Log10 fold change from baseline for each time point

Interferon-alpha:

 Systemic Interferon post dose is defined as interferon-alpha post dose > LLOQ pg/mL

Transcriptional Variables:

 Fold change from baseline for each time point calculated as 2**(Change from BL), eg, If change from BL=3 then fold change from baseline = 2**(3) =8.

PD data processing rules-

- Values below limit of quantification set to limit of quantification for cytokine and neopterin derived variables ('<' stripped from string).
- Raw value as transmitted to Roche for cytokine and neopterin variables
- Raw value is negative of original value as transmitted to Roche for transcriptional variables

Relationship between categorical HBsAq and PD Biomarkers:

The primary efficacy parameter is the incidence of HBsAg loss (that is <0.05IU/ml) at 24 weeks post EOT.

HBsAg will be categorized as;

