5.4 APPENDIX 4 ANALYSIS DETAILS SPECIFIC TO PD-L1 LNA TREATMENT COMBINATION ARM

PD-L1 LNA treatment combination arm specific analysis are listed in this appendix.

The PD-L1 LNA treatment combination arms as follow:

- One treatment arm will evaluate a 24-week treatment duration where siRNA (200 mg Q4W) will be given during Weeks 1-24 and PDL1-LNA will be given during Weeks 13-24.
- A second treatment arm will evaluate a 36-week treatment duration where siRNA (200 mg Q4W) will be given during Weeks 1-24 and PDL1-LNA will be given during Weeks 25-36.

In both treatment arms, participants will receive their background NUC therapy for the duration of study treatment. At the end of the treatment period, participants will continue NUC treatment during the follow-up unless the NUC discontinuation criteria have been met

The detail analysis of the PBMC and FNA data will be cover in the next version of the statistical analysis plan.

Estimand for PDL1-LNA Treatment Combination:

The difference between proportions of HBsAg loss (qHBsAg <0.05 IU/mL) at week 24 follow-up in virologically suppressed adult CHB participants on established NUC therapy, with preserved liver function and without significant fibrosis/cirrhosis, treated with combination therapies

- 1) siRNA (200mg Q4W)+ PDL1-LNA + NUC, with 24 weeks treatment duration
- 2) siRNA (200mg Q4W)+ PDL1-LNA + NUC, with 36 weeks treatment duration

versus NUC, irrespective of adherence to IMP or whether prohibited medication and/or food has been taken.

The detail analysis of the PBMC and FNA data will be cover in the final version of the statistical analysis plan.

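### The SAP's Day 1 baseline rule leaves PD-L1 LNA antibody status without a baseline for every participant in the two PD-L1 LNA arms, so its ADA categories cannot be derived as written

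*SAP*

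**What the plan says.** SAP 4.1 defines baseline once, for all assessments, as the last valid value before the first study drug is given ("non-missing observation for each participant prior to first study drug administration"). SAP 4.6.1 repeats the rule for each participant assessment and ties it to a day: "prior to the first dose administration, this being study Day 1 pre-dose". If there is no Day 1 value, the latest screening value is used, and "if such data are not available then the assessment baseline value will be missing for that participant".

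SAP 4.6.4 summarises ADA in two periods, baseline prevalence and incidence "after study drug administration (post-baseline incidence during both the treatment and follow-up periods". It then sorts participants into ADA positive (treatment-induced or treatment-enhanced) and ADA negative (negative throughout or treatment unaffected).

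SAP Appendix 4 gives the drug sequence in the two PD-L1 LNA arms. In the 24-week arm siRNA "will be given during Weeks 1-24 and PDL1-LNA will be given during Weeks 13-24". In the 36-week arm siRNA "will be given during Weeks 1-24 and PDL1-LNA will be given during Weeks 25-36". The appendix gives no baseline rule of its own.

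The sampling days are in the row "Plasma ADA (PD-L1 LNA") of Protocol Appendix 13-Tables 7 and 8. Footnotes to both tables say that ADA samples are drawn before dosing.

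**The concern.** The protocol's sampling schedule follows each drug's own first dose; the SAP's baseline rule follows the first dose of any study drug. When both drugs start on Day 1 the two agree. When one drug is added after 12 or 24 weeks of another, they do not: the only sample that shows antibody status before exposure to the late drug falls after the SAP's cut-off for baseline.

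At stake is the ADA assessment of the drug that is new to the platform. Exploring the effect of ADA on PK, safety, PD and efficacy is a secondary objective, and it needs each participant's ADA status first. If the rule stays as it is, someone will have to choose a workaround at programming, possibly after results have been seen.

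**Working it through.** The plan gives no figure on this point to reproduce. The check applies the SAP rule to the sampling days in the protocol.

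**Inputs**

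| Item | 24-week arm (arm 8) | 36-week arm (arm 9) | Source |
|---|---|---|---|
| First study drug | siRNA, Day 1 | siRNA, Day 1 | Protocol Appendix 13-Tables 7 and 8 |
| PD-L1 LNA starts | Week 13 (Day 85) | Week 25 (Day 169) | SAP Appendix 4; same tables |
| PD-L1 LNA ADA, treatment-period visits | Days 85, 141, 169 | Days 169, 197, 225, 253 | same tables |
| PD-L1 LNA ADA at screening or Day 1 | none | none | same tables |
| siRNA ADA at Day 1 | yes | yes | same tables |
| Planned participants | about 30 | about 30 | Protocol Appendix 6-Table 1 |

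The virological breakthrough/relapse and early termination/unscheduled columns are also ticked, but those visits come after Day 1.

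**Step 1: delay from Day 1 to the first PD-L1 LNA ADA sample**, (first sampling day − 1) / 7:
- Arm 8: (85 − 1) / 7 = 12.0 weeks.
- Arm 9: (169 − 1) / 7 = 24.0 weeks.

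**Step 2: scheduled siRNA doses before that sample**
- Arm 8: Days 1, 29 and 57, so 3 doses.
- Arm 9: Days 1, 29, 57, 85, 113 and 141, so 6 doses.

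**Step 3: apply SAP 4.6.1.** Day 1 value: not scheduled. Screening value: not scheduled. Result: missing. This holds for every participant in both arms, about 30 + 30 = 60.

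**Step 4: apply SAP 4.6.4.** Each of the four categories begins from a known baseline:
- Treatment-induced: negative at baseline, response later.
- Treatment-enhanced: positive at baseline, titre rises by a margin such as 4-fold.
- Negative: negative at baseline and at every later sample.
- Treatment unaffected: positive at baseline, no such rise.

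With baseline missing, none of the four can be met, and baseline prevalence has no observations. The Day 85 or Day 169 sample follows siRNA dosing and is therefore dated post-baseline, although no PD-L1 LNA has yet been given.

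**Step 5: the same step with a drug-specific baseline.** Day 85 (arm 8) and Day 169 (arm 9) become baseline. The scheduled post-baseline treatment-period samples are Days 141 and 169 in arm 8 and Days 197, 225 and 253 in arm 9. All four categories can then be derived.

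**The case against.** The best reply is that the intent is clear. The immunogenicity set in SAP Section 3 equates a pre-dose ADA sample with baseline, the schedule draws ADA pre-dose, and SAP 4.1 taken alone could be read drug by drug. A wholly empty baseline column would also be noticed at programming. As evidence of intent this is fair. But the analysis-set wording only decides who is included, SAP 4.6.1 names Day 1 and so closes the drug-by-drug reading, and SAP Appendix 4 does not override it.

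A second reply is that this is SAP version 1 and some detail is deferred. What is deferred is the relationship of ADA to other outcomes (SAP Appendix 3) and the PBMC and FNA analyses (SAP Appendix 4). The ADA classification in 4.6.4 is not deferred, and the relationship analysis depends on it.

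The reply does stand against three wider readings that a reader might draw:
- *Pre-existing antibody will be reported as treatment-induced.* Only if a missing baseline were treated as negative, and the SAP has no such rule. Read strictly, participants are unclassifiable, and no count of false positives can be supported.
- *Soluble PD-L1, extracellular vesicle and cytokine results in these arms would be wrong.* The SAP specifies no change-from-baseline analysis of soluble PD-L1 or vesicles. Its cytokine analysis is in the TLR7 appendix. Soluble PD-L1 is sampled on Day 1 and through the siRNA lead-in, so a display over time would show that period.
- *TLR7 has the same fault.* SAP Appendix 2 already plans "Geometric Mean and Change from baseline (baseline for the period) for each time point- tables and plots". Transcriptional fold change is computed from that change. Only the cytokine fold-change wording is loose.

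Nor is a PK baseline needed, because no PK change from baseline is planned.

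**Conclusion.** The point holds for PD-L1 LNA ADA in the two PD-L1 LNA arms. It is a stated rule that gives an unusable result, not merely an omitted detail: baseline status is missing for 100% of participants in these arms, about 60 as planned, and neither prevalence nor any ADA category can be derived for this drug. ADA to siRNA in the same arms is unaffected, because it has a Day 1 sample.

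This rests on reading SAP 4.6.1 as written, on the sampling days in Appendix 13-Tables 7 and 8, and on no unscheduled PD-L1 LNA ADA sample having been drawn before Day 1. The consequence is limited. The ADA objective is secondary and exploratory, the study is descriptive throughout, and the primary HBsAg endpoint is not touched. It is worth correcting because it costs little and removes a choice that would otherwise be made after the data are in.

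**What to change.** Add to SAP 4.6.4, with a cross-reference from 4.1 and 4.6.1:

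- For ADA, baseline is the last sample before the first dose of the drug that the assay targets. For PD-L1 LNA this is the Day 85 pre-dose sample in arm 8 and the Day 169 pre-dose sample in arm 9. For siRNA it remains Day 1 pre-dose.
- For ADA, post-baseline means after the first dose of that same drug.

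Leave the Day 1 rule in place for HBsAg and the other virology measures. Optionally, state in SAP 5.2 (Appendix 2) that TLR7 cytokine fold change uses the same period baseline as change from baseline.

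The cost is about two sentences in the SAP and one drug-specific baseline flag in programming. No new samples or visits are needed.

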4.2 PRIMARY ENDPOINTS/ESTIMANDS ANALYSES

4.2.1 Definition of Primary Endpoint(s)/Estimand(s)

Definition of Primary Endpoint:

The primary endpoint is HBsAg loss (qHBsAg <0.05 IU/mL) at week 24 post EOT.

The primary endpoint is calculated for each treatment arm as:

% participants with HBsAg loss= (Number of participants with HBsAg loss / total number of participants) *100

The percentage of participants with HBsAg loss will analyzed using evaluable patients from the mITT population.

Definition of Primary Estimand:

In line with the Estimands addendum to ICH E9, the primary efficacy estimand is defined as follows-

The difference between proportions of HBsAg loss (qHBsAg <0.05 IU/mL) at week 24 follow-up in virologically suppressed adult CHB participants on established NUC therapy, with preserved liver function and without significant fibrosis/cirrhosis, treated with

^{**} Evaluate numerical and longitudinal data to understand the discrepancy.

^{***} Depending on numerical values, these may be rare cases of double positive (HBsAg and anti-HBs) usually seen from baseline. Seroconversion will need to be interpreted using longitudinal data.

combination therapy* versus NUC, irrespective of adherence to IMP or whether prohibited medication and/or food has been taken.

*treatment and dose levels will vary depending on the combination arm and are specified in the relevant arm specific appendix.

The primary efficacy estimand is described by the following five attributes:

- a) **Population**: Evaluable patients from the mITT population as defined in section 3. These will be CHB adult participants who are virologically suppressed for more than 6 months on established NUC therapy as defined by the inclusion and exclusion criteria listed in Protocol WV41073 section 5.
- **b) Primary Endpoint**: % participants with HBsAg loss (qHBsAg <0.05 IU/ml) at 24 weeks post-EOT.
- c) Population level summary: The difference between proportions of HBsAg loss (qHBsAg <0.05 IU/mL) between NME combination over the control arm at week 24 post-EOT
- **d)** Treatment conditions: Treatment and dose levels will vary depending on combination arms and are specified in the relevant arm specific appendix.
- e) Intercurrent Event (ICE):

Table 5 Intercurrent Events Impacting Primary Analyses:

Intercurrent Events	SDR/ NSDR	Estimand Approach
Participants with dose interruptions or switching dose/frequency	SDR	Treatment Policy
Withdrawal from study treatment due to any medical condition or AEs/laboratory abnormalities	SDR	Treatment Policy
Investigator or Sponsor determines that treatment discontinuation is in the best interest of the participant.	SDR	Treatment Policy
Withdrawal from study treatment due to participant's withdrawal of consent, pregnancy, non- compliance with study requirement, or lost to follow-up	NSDR	Treatment Policy
Participants who take prohibited medication and food and continue in the study (List of prohibited	SDR	Treatment Policy

medication and food provided in Table 4)		
COVID-19 related ICE A) Systematic disruptions: i) Discontinued study treatment due to covid19 disruptions ii) Discontinued study due to covid19 disruptions iii) Study treatment interruption due to covid19 disruptions iv) Missed dose(s) with potentially major impact on the efficacy due to covid19	NSDR	Treatment Policy
B) COVID-19 infection related ICEs; i) Covid19 infection and concomitant medication ii) Use of the prohibited medicine or therapy iii) Death due to covid19		
Patients who met the NUC d/c criteria at EOT (or in the follow-up period) but did not stop NUC.	SDR	Treatment Policy

SDR- Study Drug Related, NSDR- Non study drug related

A "treatment-policy strategy" will be used accounting for each type of intercurrent event (ICE) as mentioned above. "treatment-policy strategy" where all observed values will be used regardless of the intercurrent event.

Table 6 List of prohibited medication and food

List of prohibited medication-

Systemic immunosuppressive drugs, immunomodulators, cytotoxic or chemotherapeutic agents, radiation therapy.

Systemic high-dose corticosteroids (e.g. >40 mg prednisolone per day) > 7 days or low-dose corticosteroids (e.g. >20 mg prednisolone per day) for > 14 days.

Arm specific prohibited medications

Prohibited food:

For CpAM, any nutrients have been taken during study which modulate activity of CYP enzymes (e.g., grapefruit-, apple-, or Seville orange-containing products).

For TLR7(3), consumption of green tea beverages during the treatment period.

CHB participants who routinely take herbal medicines which may have immunemodulatory effects

